2. Protocol Registration:

Protocol will be registered on clinicaltrials.org

3. Protocol version: 1

4. Funding:

The proposed clinical trial is self-funded.

5. Roles and responsibilities:

[name]: Department of Pediatric Dentistry and Dental Public Health Department, Faculty of Dentistry, Cairo University.

- Performs the clinical trial.
- Ensures participants' adherence throughout the trial.
- Collects the baseline data, results, interpretation and conclusions.
- Provide proper ancillary and post-trial care for all participants.
- Write the thesis.

Main supervisor & scientific advisor:

[name]. [name]: Professor of Pediatric Dentistry and Dental Public Health Department, Faculty of Dentistry, Cairo University.

- Monitors the whole process from the beginning of the trial and data collection.
- Assesses the final results and data collected from the study.
- Revises the thesis.

Co-supervisor:

[name]: Lecturer of Pediatric Dentistry and Dental Public Health Department, Faculty of Dentistry, Cairo University.

- Helps developing the protocol.
- Generates a random sequence to enroll the participants and undergoes proper allocation concealment, implementation, and access to the final data.
- Monitors the process of data collection and checks if there are any harms to the participants.
- Revises and helps in writing the thesis.

II. Introduction:

A) Background and rationale:

6.a. Research question:

In a child with cariously exposed vital primary molars, would it be better to use Collagen based pulpotomy or Biodentine based pulpotomy in terms of clinical and radiographic success of the pulpotomy procedure?

6.a. Statement of the problem:

Pulpotomy of vital primary molars is indicated when caries removal results in pulp exposure. Treatment approaches consist of devitalization using formocresol, preservation using ferric sulfate and regeneration of the remaining pulp tissue using mineral trioxide aggregate and recently Biodentine have been utilized. The ideal pulpotomy medicament would be biocompatible and bactericidal, in addition, to promoting the healing of the root pulp and be compatible with the physiological process of root resorption. (1)

Searching for more pulpotomy agents, Collagen, a protein that's present abundantly in humans, is an important component of connective tissues and performs multiple functions including wound healing.

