	3- Time elapsed till final restoration performed	Stopwatch	Continuous outcome measured in minutes

(S) Study design: Randomized controlled.

(T) Time of follow up:6 months.

8. Trial design:

Randomized controlled trial (R.C.T).

III. Methods

A) Participants, interventions & outcomes:

9. Study settings:

This study will be carried out on patients attending the out-patient clinic in Pediatric Dentistry and Dental Public Health Department-faculty of Dentistry, Cairo University, Egypt.

The procedure will be carried out by postgraduate student [name], B.D.S(2014)-Pharos University in Alexandria (PUA) and without an assistant.

10. Eligibility criteria:

Inclusion criteria:

- Children:

- 1- Aged 4 to 7, in good general health and medically free.
- 2- Cooperative patients who will comply to follow ups.
- 3- Parents provided with written informed consent.

- Teeth:

- 1- Bilaterally Carious vital primary molars with reversible pulpitis.
- 2- Restorable teeth with no more than 1/3 of root resorption.

Exclusion criteria:

- Children:

- 1- Children with medical, physical, or mental conditions.
- 2- Unable to attend follow up visits.

- Teeth:

- 1- Primary molars with any congenital anomalies.
- 2- Previously accessed teeth.
- 3- At operative procedure, haemorrhage control is unachievable after pulpotomy.

11. Interventions

The principal investigator will carry out all treatment procedures, using the split mouth technique, meaning that both groups (I & II) will be in the same patient.

For both interventions:

1. Informed consent from participating parents.
2. Baseline records photographs, percussion test, periapical radiograph, and personal data collection (Appendix 1: Diagnostic chart).
3. Allocation (concealed by withdrawing a sealed opaque envelope containing eight times folded paper containing the type of dressing material that will be used then writing patient name and ID on it and will be opened after performing the access cavity).
4. Diagnostic chart with personal, medical, and dental history will be filled (Appendix 1: Diagnostic chart).
5. Clinical examination will be performed to assess the clinical inclusion criteria. (Pulpal and periapical diagnosis is established after clinical examination).
6. Preoperative and Postoperative photographs will be taken.

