1- Survival rate (absence of any complication or complementary treatment) in terms of:

1-Absence of spontaneous pain. (Binary outcome measured with direct questioning to the patient).

2-Absence of swelling. (Binary outcome measured visually by intraoral/extraoral examination).

2- Time elapsed till final restoration performed.

13. Participant timeline:

Patients will be diagnosed to determine whether they are eligible for the inclusion criteria of this study or not.

Eligible patients will then start their treatment on the same visit.

	STUDY PERIOD					
	Enrolment	Allocation	Treatment visit	Post-treatment	Close-out	
TIMEPOINT	-t1	0	0	T1 (3m)	T2 (6m)	
ENROLMENT:						
Eligibility screen and patient selection	X					
Informed consent from participating pts	X					
Allocation (concealed in closed white envelop)	X					
INTERVENTIONS:						
The pulpotomy procedure (gaining access to the pulp)		X				
Allocation of the patient to one of the treatments groups (open the closed white envelope)		X				
Application of pulp dressing material (collagen and Biodentine)			X			
Final restoration			X			
ASSESSMENTS:						
baseline variables	1- photographs	X		X	X	X
	2- percussion test	X		X	X	X

	3- preoperative periapical radiograph	X				
	4- personal data	X				
outcome variables	Calculation of time-elapsed till final restoration			X		
	Questioning the patient about the absence of spontaneous pain	X			X	X
	Visual examination of patient to check the absence of sinus or Swelling	X			X	X
	Periapical radiograph to check the absence of periapical radiolucency, internal/ external root resorption	X		X	X	X

14. Sample size:

Sample size will be calculated.

15. Recruitment:

Patients attending the out-patient clinic in the pediatric dentistry department- Cairo University, having bilateral carious lower molars will be carefully assessed for eligibility to participate in our study by one of the main investigators [name], then a full explanation of the nature of our experiment and the importance of maintaining this primary tooth and restoring it for proper functions and the drawbacks of extracting it. Full mouth treatment will be offered for them.

B) Assignment of interventions:

16. Allocation:

16a. Random sequence generation (Randomization):

Teeth that will be included in the current trial will be randomly assigned one of the experimental groups using closed white envelopes (simple randomization 1:1 ratio).

a) Sequence generation:

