By shuffling the envelopes then selecting envelop for each patient upon their enrolment.

b) Allocation Concealment:

Using 8-time folded paper on which dressing material was written contained in the closed white envelope.

c) Implementation:

When a patient agrees to participate in the trial, an envelope will be drawn by one of the residents present at the clinic and name, telephone number and patient's ID will be written on it. Those selected envelopes will be opened at treatment visit after performing pulpotomy to choose which material should be used.

Randomization and allocation concealment will be performed by the co-supervisor to avoid selection bias.

17. Blinding:

The blinding is not possible (unfortunately) due to the nature of the trial.

Trial participants, outcome assessors and statistician will be blinded.

C)Data collection, management, and analysis:

18. Data collection methods

Baseline data collection

Plans for assessment and collection of outcomes will be at 3 and 6 months clinically (using visual examination, palpation, and percussion test with back of the mirror) and 0 and 6 months radiographically (using periapical radiograph) and will be done by two blinded assessors independently, and differences will be solved by consensus. To promote data quality, duplicate measurements by the same examiner (intra-examiner agreement) and training of assessors (inter-examiner agreement) will be done.

19. Data management:

Data will be recorded on a diagnostic chart for each patient separately and will be stored with follow up periapical radiographs.

20. Statistical methods:

Clinical and radiographic outcomes will be submitted for statistical analysis by the Statistical Package for Social Science (SPSS) program windows version 13. Results will be calculated using risk reduction (R.R.).

D) Data monitoring:

21. Monitoring

The study work results will be monitored regularly by the supervisors who will have full access to these interim results make the final decision to terminate the trial.

22. Harms

- **Bur breakage:** the bur will be replaced by a new one and treatment will be proceeded.
- **Perforation of pulpal wall or floor:** The tooth condition and size of perforation will be assessed whether the treatment will be to repair the perforation and treatment will be proceeded (the tooth will be removed from the trial) or the tooth will be extracted, and space maintainer will be performed

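### Allocation rests on a hand shuffle and a resident's draw, with no documented sequence, fixed order of use or log, so an envelope redrawn or discarded before labelling would leave no trace

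*Protocol*

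**What the plan says.** The protocol describes allocation in several places.

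- **Section 16a, opening:** teeth are to be "randomly assigned one of the experimental groups using closed white envelopes (simple randomization 1:1 ratio").
- **Section 16a(a), sequence generation:** "By shuffling the envelopes then selecting envelop for each patient upon their enrolment". Nothing else is said about how the order arises.
- **Section 16a(b), concealment:** a folded paper naming the material, in a closed white envelope.
- **Section 16a(c), implementation:** "an envelope will be drawn by one of the residents present at the clinic and name, telephone number and patient's ID will be written on" the envelope, which is opened at the treatment visit after the pulpotomy. The same section then states: "Randomization and allocation concealment will be performed by the co-supervisor to avoid selection bias".
- **Section 5, roles:** the co-supervisor "Generates a random sequence to enroll the participants".
- **Section 11, step 3:** concealment is by "withdrawing a sealed opaque envelope" holding a slip folded eight times. The child's name and ID are written on it, and it is opened after the access cavity.
- **Section 11, step 11:** children are allocated *alternatively* to one of the two groups, although the opening of section 11 says that both materials go into the same child.
- **Section 14:** the sample size is still to be calculated. No number of envelopes is given anywhere.
- **Section 23:** the supervisors audit the trial process, including allocation.

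**The concern.** Section 16a is where the protocol itself fixes the allocation method, so this is not a detail left for a later plan. As written, the order of assignments comes into being only when somebody picks an envelope. An envelope acquires an identity only when a child's details are put on it.

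Two consequences follow. The order cannot be reproduced or checked against anything. And an envelope that is drawn and put back, or discarded before it is labelled, cannot be told apart from one never touched. One operator treats every tooth and sees every material used, so allocation is the step where the protection should be firmest. Blinded outcome assessors do not help, because they guard against biased assessment and not against biased assignment.

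The conflicting descriptions add a practical problem: staff following section 5, section 11 and section 16a would not all carry out the same procedure.

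**Working it through.** **1. Passages side by side.** The plan states no figure to reproduce. The check is whether the allocation texts describe one procedure that can be audited.

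| Feature | Where stated | What it says |
|---|---|---|
| Source of the order | Section 5 | A random sequence, generated by the co-supervisor |
| Source of the order | 16a(a) | Shuffling, then selecting |
| Source of the order | Section 11, step 11 | Alternative allocation of children |
| Who acts | 16a(c) | A resident draws; the co-supervisor performs randomisation |
| Envelope | Section 11, step 3 | Sealed and opaque |
| Envelope | 16a opening, 16a(b), section 13 | Closed and white |
| Numbering, order of use, pool count, log | Nowhere | Not described |

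**2. What the trail can show.** The labelled envelope and the Appendix 1 chart (material, tooth, date) show which envelope ended with which child. Without a list, a number or a pool count, they cannot show that this envelope was the next one due, or that none was drawn and set aside before it. The section 23 audit would have nothing to reconcile against.

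**3. The label of simple randomisation.** Simple randomisation means independent assignments, each with probability 1/2. Suppose instead (an assumption, since the pool is not described) that there are N envelopes, N/2 for each material, drawn without replacement. That is a random allocation rule, and the two differ as follows.

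- Exact balance under simple randomisation has probability C(N, N/2) / 2^N. Under the fixed pool it is 1 once the pool is used up.
- A person who knows the pool is equal, and always guesses the material in excess among those left, is right on average N/2 + (2^N / C(N, N/2) − 1)/2 times. Under simple randomisation this is N/2.
- The expected number of final draws that are fully determined is 2m/(m + 1), with m = N/2.

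For N = 20, C(20, 10) = 184,756 and 2^20 = 1,048,576, a ratio of 5.675. Correct guesses are 10 + (5.675 − 1)/2 = 12.34, and 12.34/20 = 61.7%. Determined draws are 20/11 = 1.82.

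| Assumed N | P(exact balance), simple | Correct guesses, fixed pool | Determined final draws |
|---|---|---|---|
| 20 | 0.176 | 61.7% | 1.82 |
| 30 | 0.144 | 59.9% | 1.87 |
| 40 | 0.125 | 58.7% | 1.90 |
| 60 | 0.103 | 57.3% | 1.94 |

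An exact recursion over the remaining envelopes gives the same percentages and determined draws.

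**4. The 1:1 ratio.** Each child treated as planned contributes one tooth to each material. The ratio by tooth is therefore 1:1 by design, whatever the envelopes contain. Only the word *simple* is in doubt.

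**The case against.** The case for the protocol is substantial, and most of it limits what may be claimed.

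- **A shuffle is a chance mechanism.** A reader might infer that no random sequence exists at all. The documents do not support that: a proper shuffle randomises, and sections 5 and 16 both give the task to the co-supervisor. What stands is that no pre-generated, documented sequence is described.
- **Silence on numbering.** The protocol never says that the envelopes are unnumbered. It only fails to say that they are numbered.
- **Some audit trail exists.** Section 11 step 3 has the child's details written on the envelope before it is opened, Appendix 1 records material and tooth, and section 23 provides supervisor audit. It would be wrong to say that draws cannot be audited. The trail is incomplete at the point before labelling.
- **Concealment has real safeguards.** The envelope is called opaque and sealed in one place, the slip is folded, and opening is delayed until after access or pulpotomy. Closed and white is looser wording and does not by itself contradict opaque and sealed.
- ***Alternatively* may be loose English** for one or the other. The word still has to go, because strict alternation would be fully predictable and a reader cannot tell which is meant.
- **Size of bias.** It is tempting to turn the guessing rates into a false treatment difference. With an assumed 10-point gap in failure risk between the worse and better tooth, 10 × (2 × 0.617 − 1) gives about 2.3 points for 20 envelopes. That needs an equal pool, an operator who knows it is equal, consistent steering, freedom to choose which tooth the envelope governs, and the 10-point gap itself. The documents give none of these. Nor can steering a worse child favour one material when both are used in the same child.
- **Detectability.** Baseline radiographs and percussion tests are collected, so a baseline comparison might reveal some steering. The bias need not be invisible.

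**Conclusion.** The point holds as a weakness in the stated method and an inconsistency between sections. Sections 16a(a) to (c) set allocation by hand shuffle and free draw, without a documented sequence, stated numbering, fixed order, pool count or log. A redraw or discard before labelling would not be detected. The description does not agree with section 5, with section 11 step 11, or across the envelope wordings.

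That the label of simple randomisation is wrong is conditional: it follows if the envelopes are a fixed pool drawn without replacement. The 1:1 ratio by tooth is not in question.

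No size of bias can be derived from the documents. The guessing rates of 61.7% to 57.3% for assumed equal pools of 20 to 60 show only how far a fixed pool departs from 50%. The case for change rests on the better method being cheap and on an allocation, once compromised, not being repairable afterwards. It does not rest on any evidence that subversion is intended or likely.

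**What to change.** Replace sections 16a(a) to (c), before the first child is enrolled, with the following.

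1. Before recruitment, the co-supervisor, or another existing team member, generates a list by computer and keeps the seed. That person must neither enrol nor treat. Section 23 has supervisors taking part in enrolment, so the role must be settled explicitly.
2. The list assigns, within each child, which side receives which material.
3. Each assignment goes into a sequentially numbered, opaque, sealed envelope.
4. The resident takes the next number and never chooses.
5. Envelope number, child ID, date and time are logged before opening.
6. Opened and unused envelopes are reconciled with the list at close-out.

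Delete the shuffle, the free draw and *alternatively* in section 11 step 11. Replace *simple* with the name of the scheme actually used. Describe the envelopes as opaque and sealed throughout, and make sections 5, 11, 13 and 16 agree.

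The cost is one amendment paragraph, a computer list, numbered envelopes and a one-page log. No extra children, visits or staff are needed. The small downside is that the resident must follow the numerical order and complete the log.

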7. The radiographic examination will be performed by taking periapical x-ray using (parallel technique) through machine to assess the inclusion criteria. The preoperative radiograph will serve as a reference for the follow-up radiographs. Standardization of the technique to avoid any distortion in the vertical dimension and to provide reproducible images using x-ray holding device.
8. Preoperative and postoperative radiograph will be taken by parallel technique using XCP film holder (Super Bite, Hawe Neos Dental SA, Switzerland).
9. Administration of inferior alveolar nerve block (Septodont, Scandonest® 2% L Mepivacaine HCl. 2% and Levonordefrin 1:20,000 Injection, U.S.P.) at the side of the affected tooth.
10. Application of rubber dam for isolation, then a standardized pulpotomy procedure will be performed using a large sterile round end bur in a high-speed handpiece with copious irrigation, a sharp spoon excavator will remove pulpal tissues to the orifice level. Hemostasis will be achieved by the application of a wet cotton pellet to achieve complete hemostasis.
11. Children will then be allocated into either one of the groups alternatively depending on the pulpotomy medicament used as follows:
Group I (Experimental group) collagen based pulpotomy.
Group II (Control group) Biodentine pulpotomy.

Group I (Experimental group) collagen based Pulpotomy:

1. Collagen based pulpotomy will be applied (sterile medicated collagen particles, Biofil-AB, Eucare Pharmaceuticals Pvt. Ltd, Chennai, India) according to the manufacturer's instructions and gently placed over the pulp stumps to a thickness of 2 mm.

Group II (Control group) Biodentine pulpotomy:

1. Biodentine (Septodont, Saint-Maur-des-Fossés, France) will be applied according to the manufacturer's instructions and placed over the radicular pulp with the help of a suitable sterile amalgam carrier. Gentle condensation of the mix will be done in the pulp chamber with a moistened cotton pellet.

12. For both groups;

The rest of the pulp chamber will be filled with glass ionomer cement.

Tooth will then be restored with stainless steel crown (3M ESPE, St Paul, MN, U.S.A.).

12. Outcomes:

Primary outcome:

Absence of periapical radiolucency and internal/ external root resorption (Binary outcome detected with periapical x-ray by Parallel technique using XCP film holder (Super Bite, Hawe Neos DentalSA, Switzerland).

Secondary outcome:

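### The protocol gives inconsistent times for opening the allocation envelope, and one of them lets the operator know the material before judging the haemorrhage exclusion

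*Protocol*

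**What the plan says.** The protocol times the opening of the envelope, or the allocation itself, in four places:

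- Section 11, step 3: the envelope "will be opened after performing the access cavity".
- Section 11, steps 10 and 11: the coronal pulp is removed and haemostasis achieved in step 10. Step 11 then reads "Children will then be allocated into either one of the groups alternatively depending on the pulpotomy medicament used".
- Section 13, timeline: the row "The pulpotomy procedure (gaining access to the pulp") is followed by the row "Allocation of the patient to one of the treatments groups (open the closed white envelope"). Both are marked in the Allocation column at time 0.
- Section 16 c): "Those selected envelopes will be opened at treatment visit after performing pulpotomy to choose which material should be used".

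Section 10 lists an exclusion that can only be judged during the operation: "At operative procedure, haemorrhage control is unachievable after pulpotomy". Section 11 has the principal investigator carry out every procedure in a split-mouth design, with both materials in the same child. Section 17 lists participants, outcome assessors and the statistician as blinded. The operator is not on that list.

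**The concern.** Concealment has to last until the last eligibility decision has been taken. Here that decision is whether bleeding can be controlled. It rests on the operator's judgement, and the protocol sets no time limit or objective criterion for it. If the material is already known, a tooth that bleeds persistently could be excluded when one material is due and kept when the other is due. If such teeth also fail more often, the arm with the exclusions looks better than it should on the primary radiographic outcome.

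The split-mouth design adds a second route. Once the material for one tooth is known, the material for the other follows. If the second tooth's exclusion is still undecided at that moment, it is judged with the allocation known.

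**Working it through.** **Order of events.** The protocol gives no sample size, event rate or exclusion rate, so there is no figure to reproduce. The check is to set each stated time against the exclusion decision. The operative sequence in Section 11 is: access cavity, removal of coronal pulp, haemostasis, dressing. The exclusion can be judged only at the haemostasis stage.

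| Place | Stated time | Position relative to the exclusion decision |
|---|---|---|
| Section 11, step 3 | After the access cavity | Before |
| Section 13, timeline | After a row that equates pulpotomy with gaining access | Before, if that row means access only |
| Section 16 c) | After pulpotomy | Open: haemostasis is not mentioned |
| Section 11, steps 10 and 11 | After haemostasis | After |

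None of the four says that the exclusion must be decided or recorded before the envelope is opened. The Appendix 1 chart has no field for haemostasis, exclusion or time of opening, so the order actually followed could not be checked from it.

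**Second tooth.** Section 16 a) selects one envelope per patient. The protocol does not say whether both teeth are brought to haemostasis before it is opened or whether one is finished first. In the second case the material for the remaining tooth is known before its haemorrhage check, whichever of the four times applies to the first tooth.

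**Illustrative size.** All inputs are assumptions; none comes from the protocol.

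- Proportion of teeth with borderline haemostasis: q = 0.05 to 0.10.
- Failure risk: 0.40 in borderline teeth and 0.08 in the rest, the same for both materials, so the true difference is zero.
- Every borderline tooth is excluded in one arm and none in the other.

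Spurious difference = q × 0.40 + (1 − q) × 0.08 − 0.08 = 0.32q.

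- q = 0.05: 0.020 + 0.076 − 0.080 = 0.016, or 1.6 percentage points.
- q = 0.10: 0.040 + 0.072 − 0.080 = 0.032, or 3.2 percentage points.

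If excluding one tooth removes the whole pair, what matters is how often the retained arm's tooth is borderline when its partner is not. With within-child correlation φ (zero or positive) of borderline bleeding, that probability is q(1 − q)(1 − φ) / (1 − q) = q(1 − φ), and the difference becomes 0.32q(1 − φ).

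- φ = 0: 1.6 to 3.2 points, unchanged.
- φ = 0.5: 0.8 to 1.6 points.
- φ = 1: zero.

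**The case against.** The strongest defence is that Section 11 steps 10 and 11, the operative sequence itself, already put allocation after haemostasis. That stands. A reader might infer from step 3 that concealment is broken in this trial; the documents do not support that, because only one of the stated timings clearly permits it. But step 3 belongs to the same section and says otherwise. Step 11 also cannot govern unedited, since its wording could be taken to mean alternation, whereas Section 16 specifies simple randomisation.

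It can also be said that the conflict is loose terminology, because the timeline treats pulpotomy and access as one step. This weakens the idea of two deliberately different rules. It does not help the protocol, because under that reading Section 16 c) too can place the opening before haemostasis.

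The point about the second tooth depends on the order of treatment, which the protocol does not give. It holds only if the second tooth's exclusion is still undecided when the envelope is opened.

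A reader might also see a conflict between "withdrawing a sealed opaque envelope" in Section 11 and "contained in the closed white envelope" in Section 16 b). There is none: one envelope can fit both descriptions, and one is simply fuller than the other.

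Finally, the assumed failure risks have no source in the protocol, and the criterion is bleeding that cannot be controlled, not borderline bleeding. Both objections are fair, so the figures can serve only as a ceiling under the stated inputs.

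**Conclusion.** The protocol states inconsistent times for opening the envelope relative to haemostasis, and nowhere requires the haemorrhage exclusion to be settled first. Under the step 3 timing, an operator not listed as blinded makes that exclusion with the material known, so selective exclusion is possible. Under Section 16 c) it is not ruled out. Under steps 10 and 11 it is avoided, at least for the first tooth.

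The size of any bias cannot be derived from the protocol. With 5% to 10% borderline teeth, 40% against 8% failure and complete exclusion in one arm only, it is at most 1.6 to 3.2 percentage points, falling toward zero if pairs are dropped together and bleeding is correlated within a child.

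A reader might conclude that such a bias would be beyond repair. That goes too far: following the affected teeth and analysing them as allocated would address it. The matter should be corrected because the remedy is cheap and the threat avoidable, not because harm has been shown.

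**What to change.** Reconcile Sections 11 (steps 3, 10 and 11), 13 and 16 to one rule, in line with the order in steps 10 and 11:

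1. The envelope is opened only after the haemorrhage exclusion has been decided and recorded on the chart, for both teeth where they are treated together. Remove the access-cavity timing from step 3, separate pulpotomy from gaining access in the timeline, and reword step 11 so that it refers to the randomised envelope.
2. If the second tooth is treated after the envelope has been opened, it stays in the analysis under its allocated material, and any later problem with it is reported.
3. Section 22 removes teeth from the trial after a repaired perforation or a failed pulpotomy. State that a tooth removed after opening is still counted as allocated. This concerns the analysis set only and leaves clinical management as it is.
4. Add to the Appendix 1 chart a time-stamped line for the exclusion decision and the opening of the envelope.

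The cost is consistent wording and one chart line. A few technically difficult teeth will remain in the analysis.

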The investigator will be given access to data sets. All data sets will be password protected. To ensure confidentiality, data dispersed to project team members will be blinded of any identifying participant information.

30. post-trial care:

The investigator will offer full mouth treatment, post-operative care, and preventive measures to all participants.

31. Dissemination policy:

The Thesis defense will be done as the study is a part of the requirements for a master's degree in Pediatric Dentistry. Also, the results of the study will be published in Journals.

V. Appendices**Appendix 1: Chart filled for each patient in this trial:**

Patient name:

Patient ID:

Tested material:

Age:

sex:

Address:

Telephone:

Chief complain of the patient:

Pretreatment medications:

Participating tooth:

Date of material application:

Follow up		1ry outcomes assessment clinical assessment (survival rate)		2ry outcomes assessment Radiographic assessment			Final assessment “success or failure”
Time after	Date	1- Spontaneous pain	2- Swelling	3- Internal root resorption	4 - External root resorption	5- Periapical radiolucency	
3m	/ /20						
6m	/ /20						

VI. References:

- 1- izGuven SD. *Success Rates of Pulpotomies in Primary Molars Using Calcium SilicateBased Materials: A Randomized Control Trial. Biomed Res Int.* 2017;2017:7.
- 3- *Use of collagen as a biomaterial: An update - researchgate. (n.d.). Retrieved March 6, 2022, from* https://www.researchgate.net/publication/258204888_Use_of_collagen_as_a_biomaterial_An_update
- 5- J. Camilleri. “Hydration characteristics of biodentine and theracal used as pulp capping materials.” *Dent Mater.* 2014;30:709–715.

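### Section 17 contradicts itself on blinding, and the only outcome form shows the allocation, so no described procedure protects the assessor blinding claimed for a film-read primary outcome

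*Protocol*

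**What the plan says.** Section 17 of the protocol has two sentences. The first is "The blinding is not possible (unfortunately) due to the nature of the trial". The second is "Trial participants, outcome assessors and statistician will be blinded". Neither mentions the operator.

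Section 18 says that outcome assessment "will be done by two blinded assessors independently, and differences will be solved by consensus". This covers the clinical examinations and the radiographs.

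Section 19 says "Data will be recorded on a diagnostic chart for each patient separately and will be stored with follow up periapical radiographs". Appendix 1 shows that chart. Its header includes the field "Tested material". Below it is a table with rows for 3 and 6 months and columns for pain, swelling, internal resorption, external resorption and periapical radiolucency, ending in a success-or-failure rating.

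Section 11 says "The principal investigator will carry out all treatment procedures, using the split mouth technique", so the person who treats knows the material in every tooth. Section 12 makes the primary outcome a binary reading of a periapical film.

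**The concern.** Two things need repair. First, a reader of Section 17 cannot tell who is blinded. A blanket statement that blinding is not possible is followed directly by a list of three blinded parties, with nothing to reconcile the two.

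Second, if the assessors are meant to be blinded, the documents the trial will use work against it. The form that holds the results also holds the allocation, and it is filed with the films to be read. Whether a radiolucency or a resorption is present can be a matter of judgement on a borderline film. An assessor who knows the material may lean one way on such films, and disagreements are then settled by discussion, which can pass on that knowledge. The stake is detection bias in the primary comparison, in a trial that would report its assessment as blinded.

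**Working it through.** No arithmetic applies: the protocol states no figure on this point. The check sets the relevant sections side by side.

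1. **Is Section 17 consistent?** Its first sentence denies blinding and limits the denial to no role. Its second claims blinding for participants, assessors and statistician. Taken literally, they conflict. They agree only if the first is read as applying to the operator alone, and the text does not say that.

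2. **Where are outcomes recorded?** On the patient's diagnostic chart (Section 19), shown in Appendix 1. No other outcome form appears in the protocol.

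3. **Does that form reveal the allocation?** Yes. The header asks for the material, and the clinical and radiographic results sit on the same form. The chart heads its clinical columns "1ry outcomes assessment clinical assessment (survival rate)" and labels the radiographic columns secondary, the reverse of Section 12. This does not affect the present point, since the form carries both sets of outcomes and Section 18 assigns both to the blinded assessors.

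4. **Is the form kept apart from the films?** No. Section 19 stores the two together.

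5. **Does the split-mouth design matter?** Yes. Both materials are used in the same child (Section 11). Learning the material in one tooth reveals the material in the other, so one disclosure unmasks the whole within-child comparison.

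6. **Is there a safeguard elsewhere?** Section 29 removes identifying participant information from data passed to team members. That hides who the child is, not which material was used. The envelope procedure in Sections 11 and 16 conceals the assignment until the material is chosen during treatment; it does nothing for assessment at follow-up. No section describes coded films, an assessor form without the material, or an allocation record held apart from the chart.

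7. **Who are the assessors?** Section 18 gives their number and calls them blinded. Section 5 lists the investigator and two supervisors but no assessors. The protocol therefore neither makes the operator an assessor nor rules it out.

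Steps 1 to 4 are facts of the text. With step 6 they support one conclusion: the claim of assessor blinding has no described procedure behind it, and the described paperwork exposes the allocation.

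**The case against.** The strongest reply is that Section 17 merely lacks a word. The operator must know the material, the second sentence lists everyone else, and Section 18 calls the assessors blinded again. That reading is probably the intended one. It supports a rewording and does not show that assessment will be open. What remains is that the protocol does not say it.

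A reader might go further and infer that the claimed blinding does not exist. The documents do not support this. Section 19 says where data are recorded and stored, not who holds the chart during scoring. The chart has one cell per outcome and visit, while Section 18 calls for two independent readings and repeat measurements. The chart may therefore be a master record completed after consensus. It is also no evidence against the blinding of participants or statistician: both groups receive the same filling of the remaining chamber and the same type of crown. Leaving out a coded dataset is not an error in itself, since such detail commonly sits in an analysis plan or a manual.

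A reader might also infer that the operator scores outcomes, because Section 5 says of the investigator "Collects the baseline data, results, interpretation and conclusions". Collecting results is not judging them, and Section 18 gives the judging to two blinded assessors.

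These replies limit the conclusion. They do not explain why the allocation belongs on the outcome form, or what keeps it from the assessors.

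**Conclusion.** The point holds in a limited form. Section 17 contradicts itself as written and must say which roles are blinded. The only outcome form carries the allocation and is stored with the films, so nothing described protects the assessor blinding that Sections 17 and 18 claim. The text facts are certain. Whether an assessor would see the chart while scoring is not known, so detection bias is a risk left open, not a demonstrated effect.

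No size can be given. The protocol states no sample size, event rate or effect size, and nothing on how often a film is ambiguous, so any figure for the shift would rest on assumption alone. The point matters because the primary outcome is read from a film and the protection is cheap. It should be corrected before enrolment.

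**What to change.** - Reword Section 17 to say that the operator is not blinded, and that participants, the two outcome assessors and the statistician are.
- Take the material field off the outcome chart and put it on a separate allocation log that the assessors cannot access until scoring is complete. Amend Section 19 so that the films are stored with the chart without allocation and not with the log.
- Have the two assessors score films coded by patient and tooth, on a form that shows no allocation and has room for both independent readings and the consensus.
- State in Section 18 that the operator is not one of the assessors.
- Give the statistician a coded group variable.

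The cost is one form split in two and a coding step for films and data. The two assessors are already planned, so no staff are added.
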